### 2.2 Sample Size Justification

Sample size for the Allofit Ceramic PMCF Study was estimated using the McHugh and Le method [39] with an alpha (Type I) error level of 0.05, a non-inferiority margin of 5.2% ( $\delta$ ), and an assumed survival rate of 90% at 10 years from ODEP.

The confidence limit approach, as discussed by McHugh and Le [39], can be used to calculate this sample size estimate. Specifically, we infer that the non-inferiority margin provides the absolute precision (5%  $\delta$ ) for the difference between the fixed rate in the historical control group and the rate estimated for the experimental group over the course of the study. Sample size estimation utilizes the following formula:

$$\delta \sqrt{n} = Z_{1-\alpha} \sqrt{\frac{p_{\text{exp}} (1 - p_{\text{exp}})}{w_{\text{exp}}} + \frac{p_{HC} (1 - p_{HC})}{w_{HC}}}$$

where  $\delta$  represents the non-inferiority margin, n represents the group size,  $p_{exp}$  represents the rate in the experimental group,  $p_{HC}$  represents the rate in the historical control group,  $w_{exp}$ 

represents a weight (i.e., allocation weight) to accommodate unequal group size for the experimental group,  $w_{HC}$  represents the allocation weight to accommodate unequal group size for the historical control group, and  $Z_{1-\alpha}$  represents the value of a standard normally distributed random variable corresponding to a cumulative probability of one minus alpha (0.05).

When adjusting for a ceiling in the calculation, and added attrition rate of 20% there is a sample size requirement of 195 for the experimental group. A sample size of 200 is therefore planned for enrolment in this study.

Sample size was estimated using SAS v. 9.1.3 for Windows.

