#### **Exclusion Criteria**

- The patient is:
  - A prisoner
  - Mentally incompetent or unable to understand what participation in the study entails
  - A known alcohol or drug abuser
  - Anticipated to be non-compliant.
- The patient has a neuromuscular disorder, vascular disorder or other conditions that could contribute to prosthesis instability, prosthesis fixation failure, or complications in postoperative care.
- The patient has a vascular (large and small vessel disease) insufficiency.
- The patient has a neurologic condition in the ipsilateral or contralateral limb which affects lower limb function.
- The patient has a diagnosed systemic disease that could affect his/her safety or the study outcome.
- The patient is known to be pregnant.
- The patient is unwilling or unable to give informed consent, or to comply with the follow-up program.
- The patient has received an investigational drug or device within the previous 6 months.
- The patient has an active or latent infection in or about the affected hip joint or an infection distant from the hip joint that may spread to the hip hematogenously.

|                                | 
 
The patient has insufficient bone stock to fix the component. Insufficient bone stock exists in the presence of metabolic bone disease (i.e. osteoporosis), cancer, and radiation. Note: Dual Energy X-ray Absorptiometry (DEXA) may be used to assess the presence of adequate bone stock.
 
The patient has osteoradionecrosis in the operative hip joint
 
The patient has a known sensitivity or allergic reaction to one or more of the implanted materials.
 
The patient has known local bone tumors in the operative hip.
 
The patient is Grade III obese with a Body Mass Index (BMI) > 40.
 
 |
|--------------------------------|--|
| Study Design                   | Multicentre, Prospective, Non-controlled   |
| Clinical Phase                 | Post-market  |
| Sample Size                    | A total of 200 patients were planned  185 patients were implanted with the study device and included in the study  |
| Length of Study                | 12 years (2 years of enrollment (all sites) and 10 years of follow-up)   |
| Materials and Methods          | Case report forms will be completed at Pre-op, Surgery, Discharge, and the 6 month, 1-year, 2-year, 3-year, 5-year, 7-year and 10-year intervals.  |
| Data Collection                | Paper/Electronic   |

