| Statistical Reporting          | Data collected will be summarized and reported to each participating investigator. Statistical analysis will be conducted by Zimmer Biomet or its designee. Survivorship will be evaluated using Kaplan-Meier.   |
| Scores/Performance Assessments | Harris Hip Score (HHS); UCLA activity score; SF12; EQ-5D-3L, Noise questionnaire   |
| Standards                      | 
 
The PMCF is compliant with the below:
 
ISO 14155: 2020 - Clinical investigation of medical devices for human subjects - Good clinical practice. *
 
The Declaration of Helsinki (DoH) - Ethical principles for medical research involving human subjects.
 
(*) The study protocol was drafted according to another version of the ISO 14155. Adverse Event definitions and reporting are according to ISO 14155:2020.
 
   |
| Study Funding                  | Funding for this clinical study is made available by Zimmer Biomet to support clinical data collection, IRB/EC review fees and other expenses associated with the conduct and execution of this study protocol as outlined in the fully executed Clinical Trial Agreement.   |

Allofit IT Ceramic Bearing System in THA Protocol number: CME2010-24H

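### Section 2.2 gives two values for δ and a fixed control rate that still carries a variance, and its 195 after 20% attrition does not follow from the stated inputs

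*Combined protocol and SAP*

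**What the plan says.** Section 2.2 (Sample Size Justification) uses a confidence-limit formula with one-sided α = 0.05 and an assumed 10-year survival of 90%.

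- **Margin.** The opening paragraph has "a non-inferiority margin of 5.2" per cent, labelled δ. The next paragraph says "we infer that the non-inferiority margin provides the absolute precision (5" per cent), again labelled δ.
- **Control rate.** The precision is for the "difference between the fixed rate in the historical control group and the rate estimated for the experimental group". The printed formula nevertheless adds p_HC(1 − p_HC)/w_HC to the corresponding experimental term.
- **Weights.** w_exp "represents a weight (i.e., allocation weight) to accommodate unequal group size for the experimental group", and w_HC is defined in the same way. Neither is given a value.
- **Result.** After a ceiling and an "added attrition rate of 20% there is a sample size requirement of 195 for the experimental group". The section concludes: "A sample size of 200 is therefore planned for enrolment in this study".

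The Synopsis (Sample Size row) reports that "185 patients were implanted with the study device and included in the study". Its Statistical Reporting row says "Survivorship will be evaluated using Kaplan-Meier", and section 2.1 adds success percentages. Neither states a non-inferiority test or a decision rule.

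**The concern.** In the supplied text, section 2.2 is the only basis for 200 patients. A reader should be able to put the stated inputs into the stated formula and arrive at the stated number. Three things prevent that: δ has two values, the wording and the formula disagree on whether the control rate has sampling error, and several inputs are missing.

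The number also looks suspicious. The most natural reading of the formula gives 195 before any allowance for attrition, while the text says that 195 already contains it. If attrition was left out, the planned 200 would not cover the 20% loss. If the control really is fixed, 200 is well above the need. The choice therefore decides whether the stated precision can be expected at 10 years.

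**Working it through.** **Inputs from section 2.2.** One-sided α = 0.05, so Z = 1.64485; δ = 5.0% or 5.2%; survival 90%; attrition 20%. The formula has no power term.

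**Assumptions, because the section is silent.** 90% is used for both p_exp and p_HC, both weights equal 1, and n is rounded up before and after the attrition step.

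**Formula, rearranged for n:**

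n = Z² × [p_exp(1 − p_exp)/w_exp + p_HC(1 − p_HC)/w_HC] / δ²

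**Looking for the plan's 195.** With both variance terms, 0.09 + 0.09 = 0.18. At δ = 0.05, n = 1.64485² × 0.18 / 0.05² = 194.80, rounded up to 195. This matches the plan's figure, but before attrition.

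**All four readings.** For a fixed control the second term is zero, leaving 0.09.

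| Control rate | δ | n before attrition | after, n/0.8 | after, n × 1.2 |
|---|---|---|---|---|
| Sampled, equal weights | 5.0% | 194.80 → 195 | 243.75 → 244 | 234 |
| Sampled, equal weights | 5.2% | 180.10 → 181 | 226.25 → 227 | 217.2 → 218 |
| Fixed | 5.0% | 97.40 → 98 | 122.5 → 123 | 117.6 → 118 |
| Fixed | 5.2% | 90.05 → 91 | 113.75 → 114 | 109.2 → 110 |

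No after-attrition entry is 195. A two-sided Z, which section 2.2 does not use, does not help: after attrition it gives 154 to 174 with a fixed control and 308 to 347 with equal weights.

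**Can unstated inputs give 195 after attrition?** Yes.

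- w_HC = 5/3 at δ = 5.0%: 155.84 → 156, and 156/0.8 = 195.
- p_exp = 0.93 at δ = 5.2%: 155.19 → 156, and 156/0.8 = 195.
- w_HC = 1.5 at δ = 5.0%: 162.33 × 1.2 = 194.8 → 195, rounding once at the end.
- w_HC = 1.25 at δ = 5.2%: 162.09 × 1.2 = 194.5 → 195, rounding once at the end.

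**What 200 covers.** 200 × 0.8 = 160. If 195 is the number needed at analysis, that is 195 − 160 = 35 short, and 200 tolerates a loss of only 1 − 195/200 = 2.5%. With a fixed control, 160 exceeds the 98 or 91 needed.

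**Expected precision for the 185 included.** 185 × 0.8 = 148. The one-sided 95% half-widths are:

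| Patients | Fixed control, Z√(0.09/n) | Printed formula, equal weights, Z√(0.18/n) |
|---|---|---|
| 148 | 4.06 points | 5.74 points |
| 185 (no loss) | 3.63 points | 5.13 points |

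At 148 the two framings fall on opposite sides of both stated δ values.

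**The case against.** The strongest reply is that this is incomplete reporting and not a proven miscalculation. The weights exist to allow unequal group sizes, so setting them equal is the reader's choice, and the simple values shown above reach 195 after attrition. The section does not say where its ceiling is applied, and the weight convention may be set out in the cited method paper. This stands to the extent that 195 cannot be shown to be impossible, and the direction of any error is unknown. It does not rescue the text, because each route to 195 after attrition needs a value that the plan never gives.

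Two narrower replies are also fair. The 5% may be a rounding of 5.2%; even so, it moves n from 181 to 195 at equal weights. A fixed control can be seen as the limit of the printed formula as w_HC grows; but in that limit the requirement after attrition is at most 123, which is not 195 either.

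Finally, the 185 patients are already included and no described analysis uses δ, so the consequence is modest. A half-width at 148 is a binomial approximation, and the eventual Kaplan-Meier interval will show the precision achieved. Both points are right. They limit the seriousness of the problem, but the justification still needs correcting.

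**Conclusion.** The concern holds. Section 2.2 contradicts itself on δ and on the status of the control rate, and the inputs it states do not give 195 after attrition. The exact match at δ = 5.0%, 90% in both terms and equal weights suggests that 195 is the number before attrition, but does not prove it. On that reading the requirement is 244 or 234, and 200 falls short of covering the planned loss; with a fixed control, 200 is ample.

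The effect is confined to the sample-size justification and the stated precision; no estimate or decision rule in the supplied text changes. It should be fixed, but it does not threaten the study.

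The precision figures rest on the planned 20% loss and on patients as the unit. Treating 148 as the effective number is conservative, because Kaplan-Meier uses the follow-up of lost patients until censoring. The Synopsis admits bilateral surgery and bases survivorship on device removal, so hips may outnumber patients.

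**What to change.** Revise section 2.2 as follows.

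1. State one δ.
2. Say whether the control rate is fixed or sampled, and make the formula agree.
3. Give p_exp, p_HC, both weights and the attrition step (n/0.8 or n × 1.2), and restate the requirement before and after attrition from those inputs.
4. If the calculation used 90% in both terms, equal weights and δ = 5.0%, say that 195 is before attrition, that the requirement after it is 244 (n/0.8) or 234 (n × 1.2), and that 200 does not cover the 20% loss.
5. If the inputs cannot be recovered, say so; do not simply relabel 195.
6. Report the expected one-sided 95% half-width for 148 patients under the chosen framing: about 4.1 points with a fixed control, or about 5.7 by the printed formula with equal weights. State whether the unit is the patient or the hip.

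Do not enrol more patients in either case. The cost is SAP wording only, with no change to patients, data or analysis. The downside is that the stated precision may look slightly less favourable, or that the text may have to admit that the inputs are lost.
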